4.4. End of Study Definition

The end of the study is defined as the completion of the final assessment for the last subject enrolled in the study.

5. STUDY POPULATION

No new patients can be enrolled in the study.

Prospective approval of protocol deviations in recruitment and enrollment criteria, also known as protocol waivers or exemptions, are not permitted.

5.1. Inclusion Criteria

To be eligible to participate in the study, at the Baseline Visit (except as noted below):

1. Subject completed Part B of Study VTS301 (defined as having completed Visit 27/Week 52 or completed at least through Visit 13/Week 24 and required rescue option) and is continuing in Part C of Study VTS301.
2. Subject, in the opinion of the PI, should continue treatment with adrabetadex.
3. Females of childbearing potential (not surgically sterile) must use a medically acceptable method of contraception and must agree to continue use of this method for the duration of the study and for 30 days after participation in the study. Acceptable methods of contraception include barrier method with spermicide, intrauterine device, steroid contraceptive in conjunction with a barrier method, abstinence, or same-sex partner.
4. Subject or parent/guardian must provide written informed consent to participate in the study. In addition to parental consent, assent to participate must also be sought from minor children.

5.2. Exclusion Criteria

A subject is ineligible for study participation if, at the Baseline Visit:

1. Subjects discontinued from Study VTS301 for AEs or perceived lack of efficacy.
2. Subject has an unresolved SAE for which treatment with adrabetadex has been halted.
3. Female subjects who are pregnant or nursing.
4. Subjects with suspected infection of the central nervous system or any systemic infection.
5. Subjects with a spinal deformity that could impact the ability to perform a LP.
6. Subjects with a skin infection in the lumbar region within 2 months of study entry.
7. Any of the following laboratory abnormalities at the Baseline Visit:
 - a. Neutropenia, defined as an absolute neutrophil count of less than $1.5 \times 10^9/L$.
 - b. Thrombocytopenia (platelet count of less than $75 \times 10^9/L$).
 - c. Activated partial thromboplastin time or prothrombin time prolonged by greater than $1.5 \times$ the upper limit of normal (ULN) or known history of a bleeding disorder.
 - d. Aspartate aminotransferase or alanine aminotransferase (ALT) greater than $4 \times$ ULN.

- e. Anemia: hemoglobin greater than 2 standard deviations below normal for age and gender.
- f. Estimated glomerular filtration rate less than 60 mL/minute/1.73 m² calculated using the modified Schwartz formula ([Schwartz, 2009](#)) for subjects aged 4 through 17 years old or using the Chronic Kidney Disease Epidemiology Collaboration equation formula for subjects aged 18 years or older.
8. Evidence of obstructive hydrocephalus or normal pressure hydrocephalus.
9. Recent use of anticoagulants (in past 2 weeks prior to first dose [Study Day 0]).
10. Active pulmonary disease, oxygen requirement, or clinically significant history of decreased blood oxygen saturation, pulmonary therapy, or requiring active suction.
11. Subjects who, in the opinion of the investigator, are unable to comply with the protocol or have medical conditions that would potentially increase the risk of participation.

5.3. Lifestyle Considerations

For the 3 days following each dosing procedure, subjects should avoid acoustic overstimulation and minimize exposure to loud noises (eg, headphones for music or video games).

6. STUDY TREATMENT

Study treatment is defined as any investigational treatment, marketed product, placebo, or device intended to be administered to a study subject according to the study protocol.

The formulation and filling of adrabetadex involves dissolving the active pharmaceutical ingredient in water for injection, adding sodium chloride to 0.9% w/v and adjusting the pH if necessary with sodium hydroxide or hydrochloric acid, and bringing to the final volume with water for injection. The product is then filled into vials (10 mL vial with sufficient overfill to facilitate a 4.5 mL withdrawal) and autoclaved. The final formulation and fill process will be transferred to a third-party contract manufacturer for future commercial manufacturing. This will be carried out under a formal technology transfer protocol and product comparability will be assessed. The product is a clear, colorless solution that is free from visible foreign matter.

6.1. Treatment Administration

No new patients can be enrolled in the study.

Eligible subjects who transition into this study will receive treatment with adrabetadex at the last dose level administered in Study VTS301; adrabetadex will be administered IT via LP infusion every 2 weeks, for up to 3 years or until the investigator considers adrabetadex to be no longer beneficial to the subject, or the adrabetadex development program is discontinued. The IT dosing via LP will be conducted by dedicated study personnel in a dedicated room.

Adrabetadex will be administered as an IT slow bolus (1 to 2 minutes, depending on the volume administered) LP injection (maximum rate of administration = 4.5 mL/minute). The volume of the injection is determined by the dose level (see [Table 3](#)). Prior to adrabetadex injection, a volume of cerebrospinal fluid approximately equal to the adrabetadex dose is to be removed. Anesthesia or sedation will be used for the IT dosing procedure, following institutional guidelines and procedures. Subjects will be required, if possible, to lie flat for 30 to 45 minutes following dosing with feet elevated.

Table 3: Adrabetadex Dose, Injection Volume, and Concentration

Dose Level (mg)	Injection Volume (mL)	Concentration (mg/mL)
900	4.5	200
600	3.0	200
400	2.0	200

There is no control product in this study. For additional details, refer to the study manual.

6.2. Study Treatment Preparation/Handling/Storage/Accountability

Study treatment will be provided by the sponsor or sponsor's representative.

Labeling of the study drug will be in accordance with Good Manufacturing Practice and as required by local and national regulations.

The sponsor (or designee) will ship study drug to the study center. The initial study drug shipment will be shipped after study center activation (ie, all required regulatory documentation has been received by the sponsor and a contract has been executed). Subsequent study drug shipments will be made after study center request for resupply.

Adrabetadex will be provided in appropriately labeled vials (10 mL Type I white glass vial filled with 4.5 mL of adrabetadex, 20 mm FIOLAX stopper, and plastic white flip-off caps coated with FluroTec, or similar vial) formulated as a 200 mg/mL injectable solution. A pharmacist/designee at each study center will be responsible for preparing the assigned dose undiluted (ie, a 900 mg dose will be administered in 4.5 mL, a 600 mg dose will be administered in 3 mL, and a 400 mg dose will be administered in 2 mL). Study drug should be stored between 15°C and 25°C, inclusive.

The investigator or designee will confirm that appropriate temperature control conditions have been maintained during transit for all study treatments received and any discrepancies are reported and resolved prior to study treatment administration.

The study treatment will be maintained in a monitored, environmentally controlled (in accordance with treatment labeling), secure, locked area with restricted access at the study center.

During the study, the study drug will not at any time be handed out to the subjects. The designated study personnel will be responsible for the handling and administration of the study drug during the study.

In accordance with the International Council for Harmonisation (ICH) requirements, at all times the investigator will be able to account for all study drug furnished to the study center. An accountability record will be maintained for this purpose. The investigator must maintain accurate records indicating dates and quantity of study drug received, to whom it was administered (subject-by-subject accounting) and accounts of any study drug accidentally or deliberately destroyed. All unused study drug not involved in immediate subject treatment will be maintained under locked, temperature-controlled storage at the study center.

Please refer to the Pharmacy Manual for complete information regarding handling, storage, preparation, and accountability of study drug.

6.3. Measures to Minimize Bias

This is an open-label study; no measures to minimize bias are being employed.

6.4. Study Treatment Compliance

Adrabetadex will be administered at the study center by a study clinician. The amount of adrabetadex administered will be recorded and overall treatment compliance will be calculated.

6.5. Prior and Concomitant Therapy

The start and stop date, dose, unit, frequency, route of administration, and indication for all prior and concomitant medications and non-drug therapies received will be recorded. All treatments (lifetime) for NPC will be recorded.

6.5.1. Prohibited Concomitant Therapies

The following treatments will not be permitted during the study:

- Anticoagulants.
- Investigational treatments (exclusive of adrabetadex).
- Any investigational drug, device, or procedure administered as part of a research study.

If any prohibited medication is taken during the study, all pertinent information will be recorded in source documents and the electronic case report form (eCRF). The designated study medical monitor (MM) must be informed immediately so the sponsor may determine whether to continue the subject in the study.

6.5.2. Permitted Concomitant Therapies

The following treatments will be permitted during the study:

- Miglustat (ie, Zavesca or generic) maintained at a constant dose (dose adjustments for weight or as medically necessary are permitted).
- Age-appropriate multivitamins.
- Other required chronic medications as prescribed by a physician should be maintained at a constant dose throughout the study (dose adjustments for weight or as medically necessary are permitted).
- Short-term course of other medication for treatment of, eg, otitis, urinary tract infection, pain, upper respiratory infection.

6.6. Study Treatment Modification

Subjects who, in the opinion of the investigator, experience a drug-related AE after any IT treatment that is considered clinically relevant and impactful to the subject's function may have their dose of adrabetadex reduced (see [Table 4](#)).

Dose reductions should be considered for subjects who experience a drug-related AE of hearing impairment, asthenia, fatigue, lethargy, marked behavioral disturbance, ataxia, or gait difficulty that:

- Occurs after any IT treatment AND
- Is of moderate or severe intensity AND
- Does not resolve within 48 hours after dosing.

If a subject requires dose reduction due to an AE meeting the above criteria, and if a subject continues to experience an AE of note after dose reduction, the subject's dose may be reduced as described in [Table 4](#).

Table 4: Adrabetadex Dose Reductions Due to Drug-Related Adverse Events

Dose Level (mg) at Time of Adverse Event	Reduced Dose (mg):
900	600
600	400
400	Dose may only be reduced after discussion with MM on a case-by-case basis, with a lower limit of 200 mg.

The AE that led to the dose reduction must be fully documented.

7. DISCONTINUATION OF STUDY TREATMENT AND SUBJECT DISCONTINUATION/WITHDRAWAL

7.1. Discontinuation of Study Treatment

The sponsor has made a determination of a negative benefit / risk balance for adrabetadex. Subjects in this study will be allowed to continue treatment until 20 October 2021 to allow time to transition off of treatment unless there are additional time restrictions mandated by an IRB/EC or health authority. Subjects can stop treatment at any time before 20 October 2021.

Following the last dose of adrabetadex, subjects will be asked to return to the clinic or participate in a telemedicine visit for a follow-up safety visit. Procedures for the End of Study (EOS) visit and the safety follow-up visit are noted in [Table 2](#).

Permanent study treatment discontinuation is required for any of the following:

- The subject develops a concurrent medical condition that precludes further participation.
- The subject's parent or guardian, withdraws consent/assent to receive any further administration of adrabetadex.
- Subject is lost to follow-up.
- Start of new treatment/therapy for the underlying disease outside the scope of this protocol.
- The subject becomes pregnant during the active treatment phase of the study.

Additionally, the sponsor reserves the right to terminate the study at any time. Following termination of this study, there is no guarantee of continued access to adrabetadex.

Reasons for terminating the study may include, but are not limited to, the following:

- The incidence or severity of AEs in this or other studies indicate a potential health hazard to subjects.
- Emergence of any efficacy information that could significantly affect the benefit:risk ratio.
- Any unforeseen problems with the drug, including manufacturing, sourcing, etc.
- Any government health and regulatory agencies request termination.
- Violation of Good Clinical Practice (GCP), protocol, or the contract by study center staff or treating physician.
- Commercial drug becomes available for the subject within the respective region.

Discontinuation of study treatment for abnormal liver function should be considered by the investigator when a subject meets one of the conditions outlined in [Section 10.5](#).

During the annual electrocardiogram, if a clinically significant cardiac finding is identified (including but not limited to changes from baseline in QT interval corrected using Fridericia's formula) after the start of study treatment, the investigator or a qualified designee will determine if the subject can continue in the study and if any change in management is needed.

The reason for study treatment discontinuation will be recorded.

A Follow-up Visit is required for all subjects who complete their final dose of treatment or undergo early termination from the study.

7.1.1. End of Study Visit

1. Review and record any AEs or experiences.
2. Record changes to concomitant medications.
3. Perform complete physical examination.
4. Perform and record vital signs including blood pressure following 5-minute rest in supine position.
5. Perform complete neurological evaluation.
6. Perform audiologic testing.
7. Collect blood for clinical laboratory tests (chemistry, hematology, coagulation).

7.1.2. Follow-up Visit

1. Review and record any AEs or experiences.
2. Record changes to concomitant medications.

7.2. Subject Discontinuation/Withdrawal from the Study

Subjects may withdraw from the study at any time at their own request, or may be withdrawn at any time at the discretion of the investigator for safety, behavioral, compliance, or administrative reasons.

If the subject withdraws consent for disclosure of future information, the sponsor may retain and continue to use any data collected before such withdrawal of consent. If a subject withdraws from the study, the subject may request destruction of any samples taken and not tested and the investigator must document this in the study center study records.

The reason for study discontinuation/withdrawal will be recorded. A subject may be discontinued from the study for the following medical or administrative reasons.

7.2.1. Withdrawal by Subject

Subjects will be free to discontinue from the study at any time.

7.2.2. Adverse Event

If a dosed subject suffers an AE that, in the judgment of the investigator, sponsor, or MM; presents an unacceptable consequence or risk to the subject, the subject will be discontinued from study drug.

7.2.3. Death

In the event that a subject dies during the study, death will be the reason for discontinuation and the cause of death will be reported as a serious AE.

7.2.4. Lost to Follow-up

Every effort should be used to maintain contact with subjects during their participation in the study. A subject may be considered lost to follow-up if there is no response to at least 3 attempts to reach the subject by telephone and no response to a certified letter (or equivalent) sent to the last known address of the subject, if possible. Efforts to contact the subject should be noted in the source documentation.

7.2.5. Met Withdrawal Criteria

Discontinuation for safety and/or tolerability issues as outlined in [Section 7.1](#).

7.2.6. Worsening of Disease Activity

Subjects may be withdrawn if, in the opinion of the investigator, there is a lack of efficacy during the study.

7.2.7. Other

If the above reasons are not applicable, please use the “Other” option in the eCRF and provide the appropriate reason for subject withdrawal.

8. STUDY ASSESSMENTS AND PROCEDURES

Efficacy assessments (NPC-SS, Clinician CGIC) and self-reported outcomes (EQ-5D-3L) will not be collected.

8.1. Audiologic Evaluation

8.1.1. Audiologic Testing

Audiologic evaluations will be performed at times outlined in the Schedule of Study Events ([Table 1](#)).

Audiologic assessments will include: 1) behavioral assessment of pure-tone and speech thresholds, and air conduction and bone conduction thresholds, when indicated; 2) word recognition ability using test techniques appropriate for age and condition; 3) evaluation of middle ear function (tympanometry); and 4) otoacoustic emissions (cochlear function). The degree of any hearing impairment will be defined by a standard clinical pediatric scale (ie, slight, mild, moderate, moderately severe, severe, and profound). If a subject reports an increase in clinically significant hearing impairment at any post-baseline assessment, unscheduled audiologic evaluation visits will increase in regularity at the discretion of the Primary Investigator.

8.2. Safety Assessments

All safety assessments will be performed at times outlined in the Schedule of Study Events ([Table 1](#)). Additional (unscheduled) safety assessments may be performed as needed.

8.2.1. Medical and Surgical History

Medical and surgical history will be obtained at the Baseline Visit for Study VTS301. Medical history will be reviewed for this study. This will include a review of the following systems: general, dermatological, respiratory, cardiovascular, gastrointestinal, genitourinary, gynecological, endocrine, musculoskeletal, hematological, neuropsychological, immune (allergies), and head, eyes, ears, nose, and throat. Historical and current medical conditions will be recorded.

8.2.2. Neurological Examination

Neurological examinations will be performed. A complete neurological examination will be performed at the Baseline Visit and at Early Termination ([Table 2](#)).

An abbreviated neurological examination comprising assessments of eye movements, coordination, gait, and reflexes, will be conducted at other visits as noted in the Schedule of Study Events ([Table 1](#)).

Clinically significant changes in the neurological examination will be identified by the investigator, captured as AEs (if not related to medical history, underlying disease or to another

existing AE), and followed by a physician or other qualified staff until the abnormality resolves or stabilizes, or until the patient discontinues from the study for reasons other than the AE.

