8.2.3. Physical Examination

A complete physical examination will be performed at the Baseline of the Current Study Visit (Visit 1), End of Study Visit, and Follow-up Visit. This will include evaluation of the head, eyes, ears, nose, throat, neck (including thyroid), cardiovascular system (including assessment of heart (ECG), peripheral pulses, and presence or absence of edema), genitourinary system, lungs, abdomen (including liver and spleen, bowel sounds), lymph nodes, musculoskeletal system (including spine, joints, muscles) neurological system (including cranial nerves, reflexes, sensation, strength), skin, extremities, and other conditions of note.

An abbreviated physical examination will be performed at visits after baseline as specified in the Schedule of Study Events ([Table 1](#)) and will include evaluation of the following:

- Skin – general examination of exposed skin
- Chest – auscultation and percussion of lungs; auscultation of the heart
- Abdomen – palpation and auscultation
- Extremities – visual inspection

The findings of the physical examinations will be recorded. Any change from the Primary Baseline Visit physical examination that is considered clinically significant by the investigator will be recorded as an AE.

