10.3.2. Definitions

Adverse Event

An AE is any untoward or undesirable medical occurrence in a subject who is administered a study treatment, which does not necessarily have to have a causal relationship with this treatment. Examples of AEs include but are not limited to:

- Clinically significant laboratory findings.
- Clinically significant changes in physical or neurological examination findings.
- An AE occurring due to study drug overdose whether accidental or intentional.
- An AE occurring from study drug abuse.
- An AE associated with study drug withdrawal.
- An unexpected AE.

An unexpected AE is defined as an AE, the nature and severity of which is not consistent with the applicable product information in the most recent version of the Investigator's Brochure.

Serious Adverse Event

An SAE is defined as any untoward medical occurrence that at any dose results in any of the following outcomes:

- Death.
- Life-threatening AE.
- Inpatient hospitalization or prolongation of existing hospitalization.
- A persistent or significant incapacity or substantial disruption of the ability to conduct normal life functions.
- A congenital anomaly/birth defect.

Death

Death is an outcome of an event. The cause of death should be recorded and reported on the SAE Form. All causes of death must be reported as SAEs. The investigator should make every effort

to obtain and send death certificates and autopsy reports to the sponsor or designee, or state not available.

Life-Threatening Event

An AE or suspected adverse reaction is considered "life-threatening" if, in the view of either the investigator or sponsor, its occurrence places the subject at immediate risk of death. It does not include an AE or suspected adverse reaction that, had it occurred in a more severe form, might have caused death. For example, hepatitis that resolved without evidence of hepatic failure would not be considered life-threatening, even though hepatitis of a more severe nature can be fatal. Similarly, an allergic reaction resulting in angioedema of the face would not be life-threatening, even though angioedema of the larynx, allergic bronchospasm, or anaphylaxis can be fatal.

Hospitalization

Hospitalization is defined as an official admission to a hospital. Hospitalization or prolongation of a hospitalization constitutes a criterion for an AE to be serious. The following situations should not be reported as SAEs:

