A hospitalization or prolongation of hospitalization is needed for a procedure required by the protocol.

A hospitalization or prolongation of hospitalization is part of a routine procedure followed by the center (eg, stent removal after surgery). This should be recorded in the study file.

A hospitalization for a pre-existing condition that has not worsened.

Important Medical Events

Important medical events that may not result in death, be life-threatening, or require hospitalization may be considered serious when, based upon appropriate medical judgment, they may jeopardize the subject or the subject may require medical or surgical intervention to prevent one of the outcomes listed above. Examples of such medical events include allergic bronchospasm requiring intensive treatment in an emergency department or at home, blood dyscrasias or convulsions that do not result in inpatient hospitalization, or the development of drug dependency or drug abuse.

AEs (serious or nonserious) that commonly occur in the study population or background regimen will be considered anticipated events. Such events include known consequences of the condition under investigation (eg, symptoms, disease progression) and other events that may be common in this study population. Anticipated events are to be recorded on the eCRF and reported as SAEs when serious. These SAEs will not be expedited to health authorities, but rather, included in aggregate safety reports.

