10.3.3. Adverse Event and Serious Adverse Event Classifications

Study Drug Relatedness

Table 5 summarizes the classifications to be used when evaluating the relationship of AEs or SAEs to study treatment.

Table 5: Adverse Event Relationships to Study Treatment

Relationship	Definition
Unrelated	An event that can be determined with certainty to have no relationship to the study drug.
Unlikely Related	An event with a temporal sequence from administration of the drug that makes a relationship improbable (but not impossible); underlying disease or other concurrent therapies provide plausible explanation.
Possibly Related	An event that follows a reasonable temporal sequence from administration of the drug; that follows a known or expected response pattern to that suspected drug; but that could readily have been produced by a number of other factors.
Probably Related	An event that follows a reasonable temporal sequence from administration of the drug; that follows a known or expected response pattern to the suspected drug; that is confirmed by stopping or reducing the dosage of the drug; and that is unlikely to be explained by the known characteristics of the subject's clinical state or by other interventions.
Definitely Related	Previously known toxicity of agent; or an event that follows a reasonable temporal sequence from administration of the drug; that follows a known or expected response pattern to the suspected drug; that is confirmed by stopping or reducing the dosage of the drug; and that is not explained by any other reasonable hypothesis.

Severity Assessment

The NCI-CTCAE Version 4.03 should be used to assess and grade AE severity, including laboratory abnormalities judged to be clinically significant. If the experience is not covered in the AEs of special interest/hearing impairment (special interest hyperlink), the guidelines shown in **Table 6** should be used to grade severity.

Table 6: Adverse Event Severity Grades

Grade	Definition
Mild (1)	Transient or mild discomfort; no limitation in activity; no medical intervention or therapy required. The subject may be aware of the sign or symptom but tolerates it reasonably well.
Moderate (2)	Mild to moderate limitation in activity, no or minimal medical intervention/therapy required.
Severe (3)	Interferes significantly with subject's usual function and activities.

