10.3.4. Adverse Event and Serious Adverse Event Recording and Reporting

AEs and SAEs will be recorded from signing of the ICF through completion of the last Follow-up Visit. The investigator is required to record the AE or SAE regardless of the severity of the event or its relationship to study treatment. The investigator must follow up on all AEs and SAEs reported to have occurred through the last Follow-up Visit until the event has resolved or stabilized or at such time the investigator refers the subject to a nonstudy physician. The investigator will document the further follow-up information in the subject’s source document.

During the period specified above, the investigator will:

- Record all AEs and SAEs from the signing of the ICF through the completion of the last Follow-up Visit.
- Report all SAEs on an SAE Report Form to Mallinckrodt Global Pharmacovigilance or designee.
- Report all pregnancies to Mallinckrodt Global Pharmacovigilance or designee on the appropriate form.
- Submit any Expedited Safety Report or Suspected Unexpected Serious Adverse Reaction from Mallinckrodt Global Pharmacovigilance or designee to the IRB/IEC.

The reporting requirements for AEs are summarized in [Table 7](#).

Table 7: Reporting Requirements for Adverse Events

Seriousness	Reporting Time	Type of Report
All Serious	Within 24 hours of first knowledge of event	Initial report on the SAE Form, appropriate eCRF, and source document
	Within 24 hours of receipt of follow-up information	Follow-up report on the SAE Form, appropriate eCRF, and source document
Nonserious	Per eCRF submission procedure	Appropriate eCRF and source document

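### Section 8.2.2 keeps neurological changes attributed to underlying disease or medical history out of AE capture, contrary to the AE definitions in Section 10.3.2

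*Combined protocol and SAP*

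**What the plan says.** Section 8.2.2 decides when a neurological finding becomes an AE. The investigator identifies clinically significant changes, and these are "captured as AEs (if not related to medical history, underlying disease or to another" AE already on record. That makes three exceptions: history, disease, and an existing AE.

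Section 10.3.2 defines an AE without requiring a causal link to treatment. Its list of examples includes "Clinically significant changes in physical or neurological examination findings", with no exception for cause. Later in the same section, AEs that are common in this population are called anticipated events. "Such events include known consequences of the condition under investigation (eg, symptoms, disease progression"), and "Anticipated events are to be recorded on the eCRF and reported as SAEs when serious". Only expedited reporting to health authorities is waived for them.

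Section 10.3.4 adds: "The investigator is required to record the AE or SAE regardless of the severity of the event or its relationship to study treatment".

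The other rules in Section 8.2, for physical examination, weight, vital signs and laboratory tests, make clinically significant changes AEs with no disease or history exception. For example, Section 8.2.3 says: "Any change from the Primary Baseline Visit physical examination that is considered clinically significant by the investigator will be recorded as an AE".

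**The concern.** The only objective is long-term safety, and AEs are a named part of its endpoint (Section 3.1). Neurological examination findings are not named there. Since Amendment 2 the NPC-SS and CGIC are no longer collected (Section 8), so AEs and examination findings are the main remaining record of a subject's neurological course.

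Section 8.2.2 asks the investigator to decide on cause before anything is recorded as an AE. In this trial that judgement is difficult. Section 2.3 describes progressive cerebellar dysfunction from NPC1 and also balance disorders that may come from the drug. Section 6.6 names ataxia and gait difficulty among possible drug-related AEs. Coordination and gait are two of the four items in the abbreviated neurological examination. There is no control group to help separate drug from disease.

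A change that stays only an examination finding gets no AE coding (Section 9.3.2), and no severity grade or relationship category (Section 10.3.3). A later reader of the AE listings could not see that the judgement had been made, and so could not revisit it.

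**Working it through.** The plan states no figure on this point, so the check sets the passages side by side.

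1. **Same subject matter.** Sections 8.2.2 and 10.3.2 both address clinically significant changes on neurological examination. Section 10.3.2 attaches no condition; Section 8.2.2 attaches three.

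2. **Underlying disease.** Take a gait worsening found at Week 52 that the investigator judges to be NPC1 progression. Under Section 8.2.2 it is not captured as an AE. Under Section 10.3.2 it is an anticipated event. The paragraph on anticipated events begins by calling them AEs, and it requires an eCRF entry, with SAE reporting if serious. A site cannot follow both rules.

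3. **Medical history.** The anticipated-events paragraph names consequences of the disease and events common in the population, but not medical history as such. Here the conflict rests on the unconditional example in the AE definition.

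4. **Precedence.** None is stated. Section 8.3 only sends the reader to Section 10.3 for further detail.

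5. **Support by implication.**
   - Section 10.3.4 requires recording whatever the relationship to treatment. It presupposes that an AE exists and does not mention relationship to disease.
   - In Table 5, the category for unlikely related events applies where "underlying disease or other concurrent therapies provide plausible explanation". This implies that such events are recorded first and attributed afterwards.
   - Section 8.2.3 overlaps only through the complete physical examination, which covers cranial nerves, reflexes, sensation and strength. The abbreviated physical examination has no neurological item.

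6. **Size.** The number of affected events would need the rate of clinically significant changes and the share attributed to disease or history. The documents give neither. The nearest countable quantity is the number of scheduled post-baseline neurological examinations per subject: 5 abbreviated (Weeks 26, 52, 78, 104, 130) plus 1 complete at End of Study, so 6. For about 7 subjects this is 6 × 7 = 42. It assumes that all subjects reach Week 156 and that the same wording applied before Amendment 2. It counts occasions on which the rule could apply, not events lost. For scale only, one subject is 1/7, or about 14 percentage points of any crude AE incidence; the plan itself provides only listings.

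**The case against.** The strongest defence is that Section 8.2.2 is the specific rule and Section 10.3.2 the general one, and that its purpose is to avoid re-recording known conditions. This does not resolve the conflict. The anticipated-events paragraph is equally specific about disease progression, and Section 8.2.2 governs clinically significant changes, which an unchanged known condition would not produce. Nor does it limit the exception to conditions that have not worsened.

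Several other points on that side stand:

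- A reader might infer that Section 10.3.4 contradicts Section 8.2.2 outright. It does not. It speaks of relationship to treatment and says how to handle an AE once there is one.
- The protocol writes a worsening limit elsewhere, for "A hospitalization for a pre-existing condition that has not worsened". That limit concerns which hospitalizations are not reported as SAEs. It shows that the distinction was available, but does not govern AE recording.
- Changes attributed to the drug are outside the exceptions, so the drug-related ataxia or gait difficulty of Section 6.6 is captured under either rule.
- The exception applies to changes found on neurological examination, scheduled six-monthly. Table 1 collects AEs at every two-weekly visit, so worsening reported there has its own route, and Section 9.3.2 lists other safety data.
- No hypothesis test rests on AE counts, and the sponsor has already judged the benefit/risk balance negative (Section 2.3). No planned decision is shown to depend on the missing records.

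These points limit the consequence. They do not remove the contradiction.

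**Conclusion.** The contradiction is real and in the current text. Section 8.2.2 excludes from AE capture what Section 10.3.2 includes, most clearly for changes attributed to the disease. The consequence is possible omission from the AE listings, or different recording of the same finding between sites, confined to changes attributed to disease or history. How many events this concerns cannot be derived.

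A reader might go further and take the 42 scheduled examinations as the amount of lost data, or conclude that drug toxicity is being filtered out. The documents support neither. The first is a ceiling on examinations. The second would require that drug effects were misattributed to disease, which is possible given the overlap but is not shown.

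Severity is minor to moderate. This assumes that sites would follow Section 8.2.2 as written; study manuals or eCRF instructions that might settle the matter are not among the documents.

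**What to change.** In Section 8.2.2, delete the exceptions for medical history and underlying disease and cross-refer to Sections 10.3.2 and 10.3.4. Any clinically significant neurological change or worsening with onset after consent to VTS302 is then recorded as an AE, and attribution to drug or disease is made in the Table 5 causality field. Keep the exception for an existing AE only as a guard against duplicates, subject to the rule in Section 10.3.3 that a change in severity closes one AE record and opens another.

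State the reference point for change, which Section 8.2.2 lacks. Sections 8.2.3 to 8.2.5 use the Primary Baseline, taken before the first VTS301 dose. That should not be the sole reference here: a subject who improved during VTS301 and then fell back to the pre-treatment level would show no change. Worsening from the subject's status at VTS302 entry must also count. Section 3.1 already defines a current-study baseline.

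The cost is a short amendment with IRB/IEC approval (Section 10.1.1) and more AE records, many of them assessed as unlikely related. The benefit reaches only subjects still in the study: enrollment is closed, and dosing ends by 20 October 2021, 252 days (252/7 = 36 weeks) after the Amendment 2 date of 10 February 2021. A further amendment would have less time than that.
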